4. TREATMENT OF SUBJECTS

4.1 Investigational product/treatment

The treatment protocol requires that infants will receive MSCs as soon as possible after confirmation of the PAIS, but no later than the end of the first week of onset of presenting clinical symptoms. Steps to be undertaken before MSC administration include:

- A bacterial culture taken from both nostrils before administration of MSCs.
 Blood samples will be collected before administration of MSCs. Blood samples are taken routinely in the hospital for clinical purposes, but some extra material (0.5-1 mL) will be collected to determine infection markers CRP, procalcitonin and complete blood count. These samples will be combined with routine blood sampling and taken from routinely placed (arterial) catheters
- 30 minutes prior to delivery of the cells, the nose will be cleaned with saline using standard procedures operative at the NICU.

After these procedures have been performed, infants will receive one dose of 50 x 10⁶ MSCs intranasally. We will use a sterile plastic (e.g. 1,0 mL) syringe containing the MSCs to slowly drip the MSCs alternatively in both nostrils. Blood samples will be collected again at 24 hours after administration of MSCs.

The syringe with MSC will be packaged at the CT-F of the UMC Utrecht and will be delivered to the NICU by the clinical research nurse.

4.2 Use of co-intervention (if applicable)

Not applicable.

4.3 Escape medication (if applicable)

Not applicable.

5. INVESTIGATIONAL PRODUCT

5.1 Name and description of investigational product(s)

Allogeneic bone marrow-derived adult MSCs obtained from the Cell Therapy Facility (CTF) of the UMCU. The CTF will obtain MSC, marrow: a cell product containing mesenchymal stromal cells derived from bone marrow. Mesenchymal stromal cells consist largely of mesenchymal stem cells. However, the International Society for Cellular Therapy (ISCT) states that 'multipotent mesenchymal stromal cells' (MSC) is the currently recommended definition for the plastic-adherent cells isolated from bone marrow and other tissues that have often been labelled as mesenchymal stem cells.(Dominici et al. 2006) We therefore decided to use the same acronym (MSC) as the active substance/cell type necessary for this study is mesenchymal stem cells.

5.2 Summary of findings from non-clinical studies

An overview of findings from non-clinical studies on MSC treatment for PAIS is given in chapter 7 of the Investigator's Brochure (IB).

5.3 Summary of findings from clinical studies

An overview of findings from clinical studies on MSC treatment for PAIS is given in chapter 8 of the IB.

5.4 Summary of known and potential risks and benefits

An overview of findings on potential risks and benefits of MSC treatment for PAIS is given in chapters 7 and 8 of the IB.

In summary, we have shown in our own mouse models of neonatal ischemic infarction that intracerebral application of murine adult bone marrow-derived MSCs markedly improves outcome. Treatment with MSC reduced infarct size by >45%, stimulated formation of new neurons and oligodendrocytes, partially restored cortico-spinal motor tract activity, and improved sensorimotor outcome.(van Velthoven et al. 2010c; van Velthoven et al. 2010a) Additionally, our findings indicate that MSCs can be successfully and rapidly administered to the brain via an efficient non-invasive route, the nasal route.(Donega, van Velthoven, Nijboer, van Bel, et al. 2013) The MSCs subsequently accumulate predominantly in the infarcted area. Notably, MSCs delivered via the nasal route reduce infarct size and improve motor function to the same extent as MSCs administered intracranially.(van Velthoven et al. 2010b)

In general, risks or adverse events related to MSC treatment can be categorized in three groups: acute, subacute and longterm adverse events.

- 1. Acute adverse events: Administration Reaction/Toxicity
 - Systolic blood pressure >33% decrease or increase from the baseline during or directly following the intranasal administration of the investigational product
 - Diastolic blood pressure >25% decrease or increase from baseline during or directly following the intranasal administration of the investigational product
 - Heart rate >33% decrease or increase from baseline during or directly following the infusion of the investigational product
 - Development of dyspnoea, vomiting, flushing, diarrhea, during or within 1 hour from the intranasal administration of the investigational product
 - Fever ≥ 2 grade increase from baseline during or within 2 hours from the intranasal administration of the investigational product
 - Development of exanthema, or urticaria developing during or within 2 hours from the intranasal administration of the investigational product

Allogeneic hUCB-derived MSC treatment in preterm infants with BPD appeared to be safe and without any acute adverse events.(Chang et al. 2014; Henckel et al. 2015) A large meta-analysis on clinical trials for numerous diseases did not show any evidence for acute severe toxicity due to MSC transplantation.(Lalu et al. 2012) This analysis used both adult and pediatric trials to report on a total of 1012 patients. Including eight randomized control trials, there was no association detected between MSC transplantation and acute infusional toxicity and organ system complications. There was a significant increase in fever with MSCs compared to the control group, but the fever was reported to be transient in all trials.(Lalu et al. 2012)

- 2. Subacute adverse events:
 - Bacteremia due to bacterial contamination of product. Fever ≥ 2 grade increase from baseline during or within 2 hours from the intranasal administration of the investigational product AND product contamination proven by positive product cultures. In case of contamination patients will be treated with antibiotics in case this is required. As described in the IMPD, there will be extensive quality control in the CTF, e.g. testing for contamination of the product. This risk is therefore considered to be minimal.
 - Systemic infection (e.g. meningitis) due to use of MSCs. We have no evidence from preclinical trials, nor from trials in adult stroke or neonatal BPD, that

MSC treatment increases the risk of infections. However, MSCs might be able to change inflammatory status. In order to monitor more closely, we will take extra blood samples from all subjects at baseline and 24 hours following MSC administration to determine infection markers such as CRP, procalcitonine and complete blood count.

Post-administration virus infection. This risk is minimal and adherent to all blood (derived) product administration. If a patient develops a new viral infection that is suspected to be due to transfusion of blood products or intranasal administration of the investigational product, a lookback procedure should be initiated by the treating physician according to local regulations for all blood products received. If a MSC donor is proven to be the source of virus infection, this shall be considered a serious adverse event. All donors are being screened for infectious disease markers as indicated by the Wet Veiligheid en Kwaliteit Lichaamsmaterialen (WVKL), the transposition into Dutch Law of the EU Directive 2006/17. Please find specification of control of drug stubstance in chapter 2.1.S.4.1 of the IMPD.

Allogeneic hUCB-derived MSC treatment in preterm infants with BPD appeared to be safe and without any acute or subacute adverse events. (Chang et al. 2014; Henckel et al. 2015) Also from literature on MSC treatment for adult stroke it was shown that MSC treatment has no known risks. (Bang et al. 2005; Honmou et al. 2011) A large meta-analysis on clinical trials for numerous diseases did not show any evidence for severe subacute adverse effects due to MSC transplantation. (Lalu et al. 2012) This analysis used both adult and pediatric trials to report on a total of 1012 patients with ischemic stroke, Crohn's disease, cardiomyopathy, myocardial infarction, Graft-versus-host disease (GvHD) and healthy volunteers. Including eight randomized control trials, there was no association detected between MSC transplantation and organ system complications or infections.

3. Long-term adverse events: Ectopic tissue formation and tumorigenicity

Although concerns that MSCs might transform into tumorigenic cells still exist, there is a general agreement that bone-marrow-derived MSCs can be safely cultured in vitro with no risk of malignant transformation.(Bernardo et al. 2007; Uccelli et al. 2008) So far, there have been no reports in humans of the formation of tumors by in vitro-cultured cells, thus making MSCs amenable for use in transplantation.(see IB and (Lalu et al. 2012)) This is also shown in table 1 of the IB: none of these studies have reported tumorigenesis related to MSC transplantation.

It is also advantageous that MSCs disappear within a short time frame, i.e. do not integrate in the brain, thereby limiting the ability to lead to tumor formation.

From animal models of neonatal stroke we can conclude that no adverse effects have been described for MSC treatment. Our research group has also assessed long-term safety of intranasal MSC treatment. (Donega et al. 2015) At 14 months following HI no significant lesions or neoplasia were observed in the nasal tubinates, brains or other peripheral organs of mice treated intranasally with MSCs. Additionally, it has been shown that MSCs improved sensorimotor and cognitive function for at least 9 and 14 months, respectively. These results provide strong evidence of long-term safety (and efficacy) of MSC treatment following neonatal HI in mice. (Donega et al. 2015) Also a large metaanalysis on MSC treatment for various pathologies does not support tumorigenicity of MSC.(Lalu et al. 2012) Table 1 from the IB summarizes several other studies that performed administration of autologous and allogenic bone marrow derived MSCs in the treatment of several diseases. From these studies with a follow-up time of 2 months to 4 years, it was shown that (adult) patients do not have an increased risk of long-term effects, including tumorigenicity, after allogeneic MSC treatment.

Risk-benefit balance

We can conclude that MSC treatment in newborns with PAIS might be beneficial and no subacute and long-term risks are to be expected based on available evidence. Acute administration reactions, such as subacute temperature increases, are potentially to be expected, but these are expected to be transient, self-limiting and unharmful, based on the available evidence. However, this is the first study in which MSCs will be administered intranasally in humans, so potential risks might be unknown and/or unexpected. Therefore we have planned to perform a pilot (phase I/II) trial to assess safety and feasibility of MSC treatment in newborns with PAIS. Using close monitoring and (preventative) planned actions, as described in chapter 11.1e and 11.2, and tightly regulated stopping rules (see chapter 6.7) we expect to minimize or prevent risks.

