However, the results from adult trials can be used to support safety and feasibility of MSC treatment in neonatal stroke. Clinical trials with MSC treatment for adult patients with ischemic stroke have shown some evidence for the efficacy of MSCs in the treatment of ischemic stroke. These studies described patients who were treated with MSC at 7-133 days post-stroke.(Bang et al. 2005; Honmou et al. 2011) Although the evidence is sparse, there are some trials, mainly uncontrolled open-label studies, that have demonstrated clinical neurological improvement in patients with acute and chronic stroke after treatment with MSCs.(Bang et al. 2005; Lee et al. 2010) Most importantly, these trials have not demonstrated any serious adverse events, such as neurological deterioration, systemic infections nor tumor development, related to MSC transplantation. This is also concluded from a meta-analysis on over 1200 patients treated with MSCs for various pathological indications. Only transient fever within the first days seemed to be related to MSC transfusion.(Lalu et al. 2012)

There is only one clinical trial describing the use of MSCs in treatment of neonates.(Chang et al. 2014) Chang et al. assessed in a phase I dose-escalation trial the safety and feasibility of intratracheal administration of allogeneic umbilical cord-derived MSCs in preterm infants with high risk for bronchopulmonary dysplasia (BPD). Importantly, there were no serious adverse events or toxicity related to a higher dose of 2 x 10⁴7 cells/kg.(Chang et al. 2014) These

findings were more recently confirmed by another group treating 3 premature infants with approximately 2 x 10⁶/kg bone marrow-derived MSCs intravenously.(Henckel et al. 2015) The authors concluded that intravenous MSC treatment was feasible, well tolerated and no effects on pulmonary and cerebral blood flow could be detected.(Henckel et al. 2015) An ongoing study in Korea is treating preterm infants with intraventricular hemorrhage with allogeneic umbilical cord MSCs, and preliminairy results are promising and show no adverse effects.(Presented at Pediatric Academic Societies Meeting, Baltimore, Monday May 2, 2016 - 8:00 am, E-PAS2016:3090)

Overall, MSC treatment under several pathologic conditions, including stroke, in adults and children appeared to be safe.

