As described in chapter 8 of the IB, there are many other clinical trials in adults in which MSC are used for the treatment of several diseases. Although the hypothesized mode of action of MSCs in different pathological conditions varies, the most important findings from these clinical trials refer to safety issues. In none of the trials serious adverse events related to MSC treatment were detected during bone marrow harvesting and administration. Some studies reported mild allergic reaction(Duijvestein et al. 2010), probably related to preservation substances in the MSC-product, or self-limiting fever within a few hours after MSC-transplantation. (Shi et al. 2012) In some studies patients had a serious adverse event, most likely not related to MSC administration. (Forbes et al. 2014; Wang et al. 2013; Weiss et al. 2013; Haack-sørensen et al. 2014) Additionally, a large meta-analysis on clinical trials for numerous diseases did not show any evidence for severe adverse effects due to MSC transplantation.(Lalu et al. 2012) This analysis used both adult and pediatric trials to report on a total of 1012 patients with ischemic stroke, Crohn's disease, cardiomyopathy, myocardial infarction, GvHD and healthy volunteers. Including eight randomized control trials, there was no association detected between MSC transplantation and acute infusional toxicity, organ system complications, infection, death or malignancy. There was a significant increase in fever with MSCs compared to the control group, but the fever was reported to be transient in all trials and most often low grade (≤38°C).(Lalu et al. 2012)

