- Development of dyspnoea, vomiting, flushing, diarrhea, during or within 1 hour from the intranasal administration of the investigational product
- Fever ≥ 2 grade increase from baseline during or within 2 hours from the intranasal administration of the investigational product
- Development of exanthema, or urticaria developing during or within 2 hours from the intranasal administration of the investigational product
- 2. Subactue adverse effects:
 - Bacteremia due to bacterial contamination of product. Fever ≥ 2 grade increase from baseline during or within 2 hours from the intranasal administration of the investigational product AND product contamination proven by positive product cultures. In case of contamination patients will be treated with antibiotics in case this is required.
 - Systemic infection (e.g. meningitis) due to use of MSCs. We have no evidence from preclinical trials, nor from trials in adult stroke or neonatal BPD, that MSC treatment increases the risk of infections. However, MSCs might be able to change inflammatory status. In order to monitor more closely, we will take extra blood samples from all subjects at baseline and 24 hours following MSC administration to determine infection markers such as CRP, procalcitonine and complete blood count.
 - Post-administration virus infection. This risk is minimal and adherent to all blood (derived) product administration. If a patient develops a new viral infection that is suspected to be due to transfusion of blood products or intranasal administration of the investigational product, a lookback procedure should be initiated by the treating physician according to local regulations for all blood products received. If a MSC donor is proven to be the source of virus infection, this shall be considered a serious adverse event. All donors are being screened for infectious disease markers as indicated by the Wet Veiligheid en Kwaliteit Lichaamsmaterialen (WVKL), the transposition into Dutch Law of the EU Directive 2006/17. Please find specification of control of drug stubstance in chapter 2.1.S.4.1 of the IMPD.
- 3. Long-term effects: Ectopic tissue formation and tumorigenicity

Although concerns that MSCs might transform into tumorigenic cells still exist, there is a general agreement that bone-marrow-derived MSCs can be safely

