11.2 Synthesis

Adverse events, observed by the attending physician, which are expected or possibly related to the infusion of the product, are reported to the head of the CTF. Adverse events will be reported in a database, including patient characteristics and product characteristics. Adverse events will be evaluated with the Medical Director of the CTF in their weekly meetings. We will report the observed adverse events to the Dutch Health Inspectorate. Serious adverse events will be reported within 48 hours after the event has happened.

Planned pharmacovigilance actions for potential risks

1. Acute adverse effects: Administration Reaction, during and shortly after administration Planned actions:

 Monitoring of heart rate and blood pressure. And development of dyspnoea, nausea/vomiting, flushing, diarrhea, during or within 1 hour from the administration of the investigational product

- Monitoring temperature during or within 2 hours from the administration of the investigational product. During admission, temperature will be monitored very strictly, because hyperthermia after hypoxia-ischemia is associated with adverse (neurologic) outcome.(Laptook et al. 2008; Perlman 2006) If the temperature rises above 37.5°C we will use routinely clinical used precautions to prevent actual hyperthermia, such as lowering environmental temperature or use paracetamol.
- Development of exanthema or urticaria developing during or within 2 hours from the administration of the investigational product.

2. Subactue adverse effects:

Bacteremia due to bacterial contamination of product.

Planned actions: Monitoring of temperature during the following hours to days after intranasal administration. In case of contamination patients will be treated with antibiotics in case this is required.

Systemic infection due to use of MSC therapy

Planned actions: Close monitoring of first three patients by extra blood sampling and determination of infection markers. In case of systemic infection patients will be treated with appropriate antibiotics in case this is required, according to the antibiotics protocol used on the NICU.

• Post-administration virus infection.

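### The two-hour fever criterion that gates product-related bacteraemia conflicts with the protocol's own monitoring window and fever timing, so contamination and fever events risk being misclassified

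*Combined protocol and SAP*

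**What the plan says.** Section 5.4 lists, among acute administration reactions, "Fever ≥ 2 grade increase from baseline during or within 2 hours from the intranasal administration of the investigational product". Under the subacute heading, bacteraemia from product contamination reuses that criterion and adds a second condition, so that the fever must occur during or "within 2 hours from the intranasal administration of the investigational product AND product contamination proven by positive product cultures". Section 11.1e repeats both entries. A blood culture from the infant is not part of the definition, and 'grade' is not explained.

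Other sections bear on the same events:

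- Section 11.2, planned action for contamination: "Monitoring of temperature during the following hours to days after intranasal administration".
- Section 11.2, planned action for acute reactions: above 37.5°C, "we will use routinely clinical used precautions to prevent actual hyperthermia, such as lowering environmental temperature or use paracetamol".
- Section 11.1e, on a meta-analysis of MSC trials: "fever was reported to be transient in all trials and most often low grade", with low grade given as 38°C or below. The same section mentions self-limiting fever a few hours after transplantation.
- The Rationale, on that meta-analysis: "Only transient fever within the first days seemed to be related to MSC transfusion".
- Section 2.4 refers to 11.1e for all potential risks and names administration reactions and bacteraemia among five categories.
- Section 8.1 reports SAE occurrence, toxicity included, as percentages and refers to chapter 11.1.

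**The concern.** One fever rule does two jobs, and its window suits neither well. As a gate on bacteraemia it closes at 2 hours, although the heading is subacute and the planned temperature watch runs on into later days. As a reaction criterion it may sit above the fever that the protocol itself describes as typical.

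This is a first study of intranasal MSCs in humans, with 10 infants and no control arm, and safety is its purpose. A report of no administration fevers and no product-related bacteraemia could then partly reflect the definitions rather than the product. The definitions also sit in the chapter that Section 8.1 cites for safety reporting.

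**Working it through.** No sample size, error rate or event count in the plan depends on this criterion, so there is no planned figure to reproduce. The check compares passages and then does threshold arithmetic.

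**Step 1: window (independent of what 'grade' means).**

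- Definition in 5.4 and 11.1e: during dosing to 2 hours after.
- Temperature watch for the same risk in 11.2: hours, extending to days.
- Reported MSC fever: a few hours (11.1e) or the first days (Rationale).

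The few-hours figure overlaps the definition in part. The other two extend well beyond it. A fever that starts after 2 hours can never qualify.

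**Step 2: effect of the AND.** Suppose the product culture is positive.

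- Qualifying fever at 1 hour: a bacteraemia case, even without a positive infant blood culture.
- The same fever at 12 hours: not a case.
- A smaller rise at 1 hour: not a case.
- Infant blood culture positive at 12 hours, no qualifying fever in the first 2 hours: not a case under this entry.

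The rule can therefore exclude culture-proven events and can also include events without infant culture evidence.

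**Step 3: height.** Two assumptions: 'grade' means °C, and baseline lies between 36.0 and 37.5°C. Threshold = baseline + 2.

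| Baseline (°C) | Threshold (°C) | Threshold - 38.0 | Threshold - 37.5 |
|---|---|---|---|
| 36.0 | 38.0 | 0.0 | 0.5 |
| 36.5 | 38.5 | 0.5 | 1.0 |
| 37.0 | 39.0 | 1.0 | 1.5 |
| 37.5 | 39.5 | 1.5 | 2.0 |

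A 38.0°C fever qualifies only from a baseline of 36.0°C or lower. Over 36.5-37.5°C the threshold is 0.5-1.5°C above the top of the range described as most frequent, and 1.0-2.0°C above the level at which temperature control starts. If 'grade' means a toxicity grade, this step cannot be computed, because no scale is given.

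**Step 4: illustration (every input assumed).** Let 30% of infants have an MSC-related fever, let 10-75% of fevers start within 2 hours, and let 10-50% reach the threshold, with timing and height independent.

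- Share of fevers classed as reactions: 0.10 × 0.10 = 1% to 0.75 × 0.50 = 37.5%.
- Chance of at least one classed reaction in 10 infants: 1 - (1 - 0.30 × 0.01)^10 = 3% to 1 - (1 - 0.30 × 0.375)^10 = 70%.
- Chance of at least one actual fever in 10 infants: 1 - 0.70^10 = 97%.

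The range is wide and has no support in the documents. It shows only that a count of zero reactions would be weak evidence of no fever.

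**Step 5: weight of one case.** 1/10 = 10 percentage points.

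**The case against.** The strongest reply is that these entries belong to a risk summary and little depends on them. Much of that stands, and it rules out several stronger readings.

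- *Events would be missed.* The documents do not support this. Section 7.2.1 records all adverse events, related or not. Section 6.1.2 tests for bacteraemia and other infection at any fever or sign of infection up to 3 months. Section 2.4 takes CRP, procalcitonin and a blood count at 24 hours. Section 11.2 keeps watching temperature.
- *Attribution to the product follows the definition.* No section says so. Relatedness rests on judgement: effects that might be related (6.7), a degree of probability (7.2.3), and events the attending physician considers expected or possibly related (11.2).
- *The primary criterion or stopping rule is gated.* The SAE definition (7.2.2), the dose-limiting toxicity definition (6.1.1), the infection stopping item (6.7) and the antibiotic statement do not use the fever rule. The infant with a late positive blood culture could also be placed in the adjacent systemic-infection category, which has no threshold or window.
- *The 37.5°C level contradicts the definition.* It is a management trigger, not a competing event definition. Early control makes a 2-degree rise harder to reach but does not make it impossible.
- *Typical MSC fever cannot qualify, and fever is the only MSC effect reported.* Section 11.1e says low grade most often, not always, and also reports mild allergic reactions, probably due to preservation substances in the product. Whether fever is expected at all is unsettled: 5.4 regards temperature increases as potentially to be expected, while 11.1e does not expect fever after intranasal dosing.

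What the reply does not remove is the mismatch between a 2-hour definition and a watch lasting hours to days for the same risk, or the fact that the safety analysis points to the chapter holding that definition. Placing a contamination event under systemic infection records it but loses the product-contamination label.

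**Conclusion.** The concern holds as a problem of event classification. The window conflict is established from the text and needs no assumption: contamination with fever starting after 2 hours, or with a smaller rise, is not product-related bacteraemia under 5.4 and 11.1e. The height conflict is conditional on reading 'grade' as degrees Celsius and on the assumed baselines. On that reading, MSC fever as the protocol describes it is unlikely to count as an administration reaction.

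The effect on the primary safety criterion is indirect, through how events are named and reported under Section 8.1 and chapter 11.1. It matters because each infant is a tenth of the data and the correction is only wording.

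**What to change.** Reconcile the temperature and bacteraemia passages in 5.4, 11.1e and 11.2, and state what 'grade' means and on what scale. The choice of values is the sponsor's.

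For event classification only:

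1. Remove the 2-hour fever condition as a gate on product-related bacteraemia, and align the window with the temperature watch in 11.2.
2. Base the classification on an infant blood culture taken for clinical indication, together with evidence linking it to the product, such as the product culture. Both parts are needed: an infant culture alone would label unrelated infections as product-related, and a product culture alone would count bacteraemia without evidence from the infant.
3. Tabulate each infant's charted peak temperature change from baseline, and any temperature intervention, over the monitored NICU stay, whether or not the reaction criterion is met.

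No change to patient care is proposed. The cost is protocol wording and a few case-report-form fields filled from data already charted on the NICU. The downside is that more mild, non-specific temperature events will be listed.
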